Results: The mean age of the control group was 73.13 ± 3.54 years, and the mean age of the training group was 73.75 ± 5.16 years. In the statistical analysis between groups, the Mini-Mental State Test values were found to be statistically significant in favor of the training group ($p=0.049$). In the intra-group statistical analysis, there was a significant difference in all tests in the training group after the training, while no significant difference was found in the control group.

Conclusions: It was found out that the virtual reality application in individuals with Alzheimer's dementia increased muscle strength and decreased the fall risk. As a result, supporting the physiotherapy and rehabilitation programs with technological developments and virtual reality applications will increase the success of the treatment.

Keywords: Alzheimer's Dementia; Muscle strength; Fall; Virtual reality

Study Procedure and Protocol

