Among the 38 individuals with AD diagnosis, 1 individual was not included in the study after the first evaluation due to the MMST score lower than 18, 3 individuals were not included in the study due to the hearing and communication problems, and 2 individuals were not included because they did not want to start the study. The first evaluation of the patients was

performed before randomization. 32 individuals suitable for the criteria were included in the study (Figure 1). Randomization was performed by the sealed-envelope method. According to this method, 4 females and 12 males were determined to be in the control group, while 5 females and 11 males were determined to be in the training group.

The evaluation was completed before the intervention. The same evaluation was conducted after 6 weeks. The physiotherapist with more than 5 years of experience conducted all the evaluations. Exercise training was given by another 2-year experienced physiotherapist. The training group was trained with games from different categories such as balance and aerobic exercises with a Nintendo Wii virtual reality device 2 times a week for a period of 6 weeks, with 1 session lasting for 30 minutes, and each patient was trained with the same games. In the control group, no application was performed during this period, and routine medical treatments were continued. The training group was evaluated before and after the training, while the control group was re-evaluated at the end of the 6th week after the first evaluation. After the study was completed, the volunteers from the control group were also given training.

In order to determine the sociodemographic characteristics of individuals, the case report form included questions about name and surname, age, height, weight, body mass index, dominant side, smoking, alcohol use, previous occupation, marital status, educational status, income level, number of children, social security, special healthcare needs, number of falls in the last year, vision problems, personal history, family history, medicines used, surgeries undergone, and use of a walking stick.

Their cognitive status was evaluated by the MMST. According to the MMST, 24-30 points were considered as normal cognitive levels, 18-23 points were considered as mild cognitive disorders, and 0-17 points were considered as severe cognitive disorders.

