The data were analyzed using the SPSS 24.0 packaged software. Continuous variables were presented as mean \pm standard deviation, median (minimum and maximum values), while categorical variables as number and percentage. The suitability of the data for normal distribution was examined by the Shapiro-Wilk test. The significance test of the difference between the two means was used in comparing the independent group differences when the parametric test assumptions were provided, and the Mann-Whitney U test was used in comparing the independent group differences when the parametric test assumptions were not provided. The significance test of the difference between the two pairs was used in comparing the dependent group differences when the parametric test assumptions were provided, and the Wilcoxon two-pPaired sample test was used when the parametric test assumptions were not provided. Differences between categorical variables were analyzed by chi-square analysis. In all analyses, $p<0.05$ was accepted as statistically significant.

Results

The mean age of the individuals was 73.13 ± 3.54 years, and the mean age of the training group was 73.75 ± 5.16 years. No statistically significant difference was found between the groups in terms of age, gender, height, weight, body mass index, occupation, marital status, education level, income level, number of children, and social security ($p>0.05$).

Upon examining the MMST values, the difference between the 2 groups was not statistically significant ($p>0.05$). In the post-training measurements, the values of the training group were significantly higher compared to the control group ($p<0.05$). When the changes in the groups before and after the training were examined, no statistically significant change was observed in the control group, whereas the values of the training group were significantly higher after the treatment ($p<0.05$).

When the right and left knee extension muscle strength values of individuals with AD were examined, the difference between the 2 groups was not statistically significant before and after the training ($p>0.05$). When the changes of the groups before and after the training were examined, there was no significant change in the control group, whereas the values of the training group were significantly higher after the training ($p<0.05$).

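### The week-6 group comparisons are valid but ignore the pre-randomisation baseline of the same measure, which can cost precision and leaves part of any chance baseline gap in the result

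*Combined protocol and SAP*

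**What the plan says.** Under Study Procedure and Protocol, the first assessment was "performed before randomization. 32 individuals suitable for the criteria were included in the study", and the follow-up repeated it: "The evaluation was completed before the intervention. The same evaluation was conducted after 6 weeks". A pre-randomisation value of the same measure therefore exists for all five outcomes: MMST, right and left knee extension strength, TUG and TFES.

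The Statistical Analysis Plan names two between-group tests. The parametric one is "The significance test of the difference between the two means was used in comparing the independent group differences"; otherwise "the Mann-Whitney U test was used in comparing the independent group differences when the parametric test assumptions were not provided". Paired or Wilcoxon tests are used within groups. No covariate is named.

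The Results show how this was applied. For MMST before training, "Upon examining the MMST values, the difference between the 2 groups was not statistically significant". After training, "In the post-training measurements, the values of the training group were significantly higher compared to the control group". For knee strength, "the difference between the 2 groups was not statistically significant before and after the training", and TFES and TUG are reported the same way. Change is tested only inside each arm.

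The Abstract gives the one between-group p-value: "the Mini-Mental State Test values were found to be statistically significant in favor of the training group ($p=0.049".

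**The concern.** A post-only comparison of randomised arms is unbiased over repeated randomisations and holds its type I error. It does discard information that was already collected. Two things follow in a trial of 32 people.

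- **Precision.** If baseline predicts the week-6 value, adjusting for it narrows the interval. This matters for the four comparisons that were not significant at week 6.
- **Carry-over.** If one arm happened to start ahead, about r times that lead remains in the week-6 difference. The documents show no such gap, but a non-significant baseline test with 16 per arm is weak evidence that there was none.

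The sole significant between-group result lies 0.001 below the threshold, so a small carry-over in either direction can change how it reads.

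**Working it through.** **Inputs from the documents.** 16 control and 16 training participants (Study Procedure and Protocol); p=0.049 for MMST (Abstract); significance at p<0.05 (Statistical Analysis Plan).

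**Assumptions.** The correlation r is not given, so a range is shown. Data are taken as normal with equal SDs, and results are in SD units. The p=0.049 is taken as the week-6 MMST comparison by t-test; the text states neither.

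**The plan's own sample size.** The stated 16 per arm for d=0.9 and 80% power reproduces with a one-sided 0.05 test (exact t power 80.03%). With a two-sided 0.05 test, power at 16 per arm is 69.3%. ANCOVA would give about 69.5%, 79.8% and 92.3% at r=0.2, 0.5 and 0.7. The unstated sidedness is a separate matter.

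**1. Expected precision.**

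Post-only half-width = t(0.975, 30) × √(2/16) = 2.042 × 0.3536 = 0.722 SD.

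ANCOVA half-width = t(0.975, 29) × √(2/16) × √[(1 − r²)(1 + 1/28)], with t(0.975, 29) = 2.045.

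| r | ANCOVA half-width (SD) | Simulated trials in which the ANCOVA interval was wider |
|---|---|---|
| 0 | 0.736 | 80% |
| 0.1 | 0.732 | 74% |
| 0.2 | 0.721 | 59% |
| 0.3 | 0.702 | 38% |
| 0.5 | 0.637 | 7% |
| 0.7 | 0.526 | 0.3% |
| 0.8 | 0.442 | 0% |

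The two methods break even at r = 0.193. At r=0.5 to 0.8 the interval is expected to be 12% to 39% narrower (0.637/0.722 = 0.88; 0.442/0.722 = 0.61). In simulations of 40,000 trials per r, two-sided type I error was 0.047 to 0.052 for both the t-test and ANCOVA.

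**2. What the baseline test can exclude.** The observed gap needed for p<0.05 at baseline is the same 0.722 SD. Under randomisation the standard error of the gap is √(2/16) = 0.354 SD.

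**3. Carry-over.** The post-only difference retains r × gap. A baseline gap of 0.5 SD shifts it by 0.10, 0.15, 0.25, 0.35 and 0.40 SD at r=0.2, 0.3, 0.5, 0.7 and 0.8.

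**4. The MMST result.** p=0.049 on 30 df gives t=2.052, so d = 2.052 × 0.3536 = 0.725 SD, 95% CI 0.003 to 1.447.

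For an observed baseline gap g (training minus control):

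- adjusted difference = 0.725 − r·g
- SE = √[(30/29)(1 − r²)(2/16 + g²/30)], on 29 df

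Example with r=0.5 and g=0.25: difference 0.725 − 0.125 = 0.600; SE = √(1.0345 × 0.75 × 0.1271) = 0.314; t = 1.91; p = 0.066.

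| r | Training lead at which p=0.05 (SD) | p at g=+0.25 | p at g=−0.25 |
|---|---|---|---|
| 0.2 | 0.024 | 0.067 | 0.037 |
| 0.3 | 0.078 | 0.070 | 0.028 |
| 0.5 | 0.172 | 0.066 | 0.011 |
| 0.7 | 0.278 | 0.042 | 0.002 |
| 0.8 | 0.346 | 0.022 | <0.001 |

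All the tipping leads are well below 0.72 SD. With no gap, the adjusted p is 0.053 at r=0, 0.052 at r=0.1 and 0.049 at r=0.2; it crosses 0.05 at r of about 0.16.

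**The case against.** The strongest reply is that this is a choice about efficiency and not an error. The unadjusted tests are legitimate, no baseline imbalance is reported, and the gain depends wholly on an r that nobody outside the trial can see. For MMST, r may be low because entry was limited to scores of 18 to 24. That all stands, and it is why the point concerns precision and robustness, not validity.

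Second, the tipping leads need probabilities beside them. If the week-6 result is treated as uninformative about the gap, the chance of a training lead beyond the tipping value is about 47%, 41%, 31%, 22% and 16% at r=0.2, 0.3, 0.5, 0.7 and 0.8. Where adjustment helps most (r of 0.5 or more), MMST would stay below 0.05 in about 69% to 84% of cases. This is fair: the result is more likely to survive than not, but a 16% to 31% chance of failing is not negligible.

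Third, the MMST figures rest on p=0.049 being the week-6 t-test. If it came from Mann-Whitney, the 0.73 SD estimate and the adjusted p-values lose their basis. The general argument about the unused baseline does not depend on them.

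Fourth, at r below about 0.16 the p-value can pass 0.05 merely from the cost of the extra covariate, so crossing the threshold is a blunt criterion. This is a reason to show both estimates with their intervals. It remains fair to say that a result which fails under a standard adjusted analysis is not robust.

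Finally, valid here means the type I error of each single test. It does not cover the choice of test by Shapiro-Wilk, multiplicity across outcomes, or conclusions drawn from within-group tests.

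**Conclusion.** The concern holds. The week-6 comparisons omit a baseline that was available for every outcome. ANCOVA is expected to be more precise above r of about 0.2 and slightly less precise below it, and a narrower interval is not assured in any one trial. Whether any reported conclusion would change cannot be told from the documents: they give neither r nor baseline outcome means and SDs, and the direction of a shift in the MMST result is unknown. On the stated assumptions the MMST difference is 0.73 SD (95% CI 0.00 to 1.45), and baseline leads of 0.02 to 0.35 SD, which the baseline test could not detect, would be enough to bring its p to 0.05. This should be addressed, but it does not invalidate the analysis.

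**What to change.** For MMST, right and left knee strength, TUG and TFES, fit ANCOVA of the week-6 value on group and the baseline of the same measure. Report each adjusted difference with its 95% CI beside the existing test, and state whether the conclusions agree. Keep the existing tests; do not replace them. If the MMST result does not hold in both analyses, describe it as not robust. State which test and time point produced p=0.049. A log or rank version is optional if residuals are clearly non-normal.

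The Date of the document list records that the analysis was performed in May 2018, so label the ANCOVA post hoc. Its five p-values have no multiplicity control and should be presented as a sensitivity check, not as new confirmatory tests.

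The cost is one SPSS rerun, assuming the data are still held, and one paragraph of text. The statistical cost is one degree of freedom and a slight loss of precision if r is below about 0.19. The analysis also carries the weakness of having been chosen after the results were seen.

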The study included a total of 32 volunteers between the ages of 65-80, who stayed in Karaman Ahmet Mete Nursing Home, Elderly Care and Rehabilitation Center, with mild or moderate Alzheimer's dementia diagnosed by a neurologist. There were 90 older people in Karaman Ahmet Mete Nursing Home, Elderly Care and Rehabilitation Center. Power analysis was performed to determine the size of the sample to be included in the study. As a result of the power analysis, assuming that the effect size to be obtained between the two groups will be large ($d = 0.9$), when at least 32 individuals (at least 16 individuals per group) were included in the study, it was calculated that 80% power could be obtained at 95% confidence level (with 0.05 error margin). As a result of the power analysis, it was calculated that at least 16 individuals could be included in each group (at least 32 individuals in total). 20% risk rate was determined for the individuals who could leave the study, 3 individuals were added to each group, and the study was organized with 19 individuals in each group. However, these people were excluded from the study as 4 people were not meeting inclusion criteria, 2 people were declined to participate, and therefore the study was completed with 32 individuals (Figure 1). The study included volunteers between the ages of 65-80 with mild or moderate AD diagnosis, who did not have any difficulty or problems in communicating, who did not have any neurological diseases that disrupt balance and coordination such as a cerebrovascular event, Parkinson's disease, Multiple Sclerosis, and neurological disorder, who obtained a score of 18 - 24 points in the Mini-Mental State Test (MMST) were included in the study. Patients diagnosed with rapidly progressing dementia (infection, vascular, hematologic diseases), those who could not be contacted during the follow-up period or who did not participate in the training session, those who experienced cardiac and cerebrovascular events, endocrine disorders, fluid-electrolyte imbalance and infection, those with malignancy and those who received chemotherapy and radiotherapy that causes malignancy, delirium or depression and malignant sensory loss (those with the Semmes-Weinstein monofilament thickness of 4.56 and above), and those with a lower or upper extremity amputation at any level were excluded from the study.

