When the TFES values were examined, no difference was found between the 2 groups before and after the training ($p>0.05$). When the changes of the groups before and after the training were examined, there was no significant change in the control group ($p>0.05$), whereas the values of the training group were significantly lower after the training ($p<0.05$).

When the TUG test values were examined, there was no difference between the 2 groups before and after the training ($p>0.05$). When the changes of the groups before and after the training were examined, there was no significant change in the control group ($p>0.05$), whereas the values of the training group were significantly lower after the training ($p<0.05$).

Conclusion

Along with cognitive functions, losses in motor functions such as muscle strength, balance, coordination, and walking occur in individuals with AD. A good physiotherapy and rehabilitation program is required to prevent and treat these problems. The virtual reality environment is a computer-generated three-dimensional simulation of a real-world situation in which the user can sense and control this simulation environment sensorially by means of special devices. In conclusion, the support of physiotherapy and rehabilitation programs with technological developments and virtual reality applications will increase the success of treatment especially for muscle strength, walking speed, reduction of fall risk and cognitive functions. This training may work as well, and that the results indicate that it may reduce the risk of falls.

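### Between-group results are judged by p<0.05 alone, with no difference or confidence interval planned, and with 16 per arm the non-significant fall measures cannot support a statement of no difference.

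*Combined protocol and SAP*

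**What the plan says.** The Statistical Analysis Plan section summarises variables by mean and SD, and by median and range. It compares groups with a two-sample test of means or, where parametric assumptions fail, the Mann-Whitney U test. The only criterion is: "In all analyses, $p<0.05$ was accepted as statistically significant". No between-group difference, effect estimate or confidence interval is planned.

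The Results follow that pattern. For TFES, "no difference was found between the 2 groups before and after the training"; for TUG, "there was no difference between the 2 groups before and after the training". Each statement carries p>0.05 and nothing more. Right and left knee extension strength are described as not statistically significant. Post-training MMST is described as significantly higher in the training group, and the Abstract gives p=0.049.

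The sample size paragraph in Study Procedure and Protocol assumes a large effect, d=0.9, and states 80% power when "at least 32 individuals (at least 16 individuals per group) were included in the study". The same section gives the randomised groups by sex: "4 females and 12 males were determined to be in the control group, while 5 females and 11 males" in the training group, so 16 and 16.

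**The concern.** A p-value above 0.05 shows that the data did not exclude zero. It does not show that the groups are alike. That distinction matters most in a small trial planned around a large effect, because a real moderate effect would usually come out non-significant.

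TFES and TUG are the fall measures, and fall risk is one of the two aims in the Abstract. Without an estimate and interval, a reader cannot tell whether the between-group result points to benefit, to nothing or to harm, or how large an effect remains possible. The same gap affects the one significant result: p=0.049 gives neither the size of the MMST difference nor how near to zero its interval runs.

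**Working it through.** **Inputs.** 16 per arm, so 30 degrees of freedom (Study Procedure and Protocol); planned d=0.9, 5% level, 80% power (same section); MMST p=0.049 (Abstract). Sidedness is not stated. Differences are in SD units because the documents print no outcome means or SDs. In the examples below, a positive d favours training.

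**1. The plan's own figure.** By the normal approximation, n per arm = 2(z_α + z_β)²/d².
- One-sided 5%: 2(1.645 + 0.842)²/0.81 = 15.3, so 16. Exact t-test power at 16 per arm is 80.0%. The stated 16 reproduces.
- Two-sided 5%: 2(1.960 + 0.842)²/0.81 = 19.4, so 20 (exact t-test 20.4, so 21). Exact t-test power at 16 per arm is 69%, and the effect detectable with 80% power is d=1.02. The stated 16 does not reproduce.

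**2. Precision at 16 per arm.**
- Standard error of the difference = √(2/16) = 0.354 SD.
- 95% half-width = t(0.975, 30) × 0.354 = 2.042 × 0.354 = 0.72 SD.

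**3. What a non-significant result leaves open.** The interval is d ± 0.72.

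| Observed d | Two-sided p | 95% interval (SD) |
|---|---|---|
| 0 | 1.00 | −0.72 to 0.72 |
| 0.2 | 0.58 | −0.52 to 0.92 |
| 0.5 | 0.17 | −0.22 to 1.22 |
| 0.7 | 0.057 | −0.02 to 1.42 |
| −0.3 | 0.40 | −1.02 to 0.42 |

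Whatever the estimate, the limit on its own side of zero is at least 0.72 SD away, since |d| + 0.72 ≥ 0.72. The planned effect of 0.9 stays inside the interval whenever the observed d is non-significant and at least 0.9 − 0.72 = 0.18.

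**4. Two-sided power at 16 per arm (noncentral t).** 13% for d=0.3, 28% for d=0.5, 59% for d=0.8, 69% for d=0.9.

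**5. MMST, p=0.049, read as a two-sided t-test on 30 df.**
- t = 2.052, so d = 2.052 × 0.354 = 0.73 SD.
- 95% interval = 0.725 ± 0.722 = 0.003 to 1.45 SD.
- If the p-value was rounded from anywhere between 0.0485 and 0.0495, the lower limit is 0.005 to 0.002 SD.

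**The case against.** The strongest reply is that the documents do not act on the null wording. The Abstract's Conclusions say training reduced fall risk, and the closing Conclusion says the results indicate it may. Those statements draw on within-group change, so nobody is told that training fails. This is correct: a reader might infer that the trial concluded there was no effect on falls, and it did not. But the Results and the conclusions then point in different directions, with no between-group estimate to settle which is supported. The reply therefore adds to the case for reporting one.

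Several stronger readings should also be resisted.

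- **That the data exclude neither benefit nor harm on TFES and TUG.** Only the width of each interval is known. An observed d of 0.7 would leave almost no room for harm, and one of −0.3 would exclude the planned benefit.
- **That every non-significant result is misworded.** Only TFES and TUG are. Knee strength and baseline MMST are worded acceptably, although they too lack an estimate and interval.
- **That the MMST result is concealed.** The Abstract prints p=0.049, which shows it is borderline. What is missing is its size and interval.
- **That the MMST difference can be put in points.** The 18–24 entry window restricts baseline scores only, so it sets no limit on the SD of post-training scores.

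It is also fair to say that planned per-arm means and SDs would let a reader derive an unadjusted difference in means for a t-tested outcome. However, the plan does not ask for that difference, these documents do not print the outcome summaries, and that route would not give a Hodges-Lehmann estimate for a rank-tested outcome.

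**Conclusion.** The point holds in a limited form. The plan has one decision criterion and no between-group estimate or interval, and the Results turn two non-significant comparisons into statements of no difference. With a half-width of about 0.72 SD and 28% power for a 0.5 SD effect, p>0.05 cannot support those statements. It does not follow that an effect exists: the TFES and TUG estimates are unknown.

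The 0.72 SD figure assumes a comparison of means with all 16 per arm analysed; for a Mann-Whitney outcome it is a guide only. The MMST interval of 0.003 to 1.45 SD assumes a two-sided t-test. It is approximate if a rank test was used, and if p=0.049 was one-sided, the two-sided p would be 0.098 and the interval would include zero. The tests themselves are not invalid. The fault lies in what is reported and how it is read.

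**What to change.** 1. In the Statistical Analysis Plan, add for MMST, right and left knee extension strength, TFES and TUG the week-6 training-minus-control difference in the outcome's own units (points, kg-force, points, seconds) with a two-sided 95% confidence interval. Adjustment for the baseline value, already collected for everyone, is preferable. Where a rank test is used, give the Hodges-Lehmann shift with its 95% interval. State which direction favours training, since lower is better for TFES and TUG.
2. In the Results, replace "no difference was found between the 2 groups before and after the training" (TFES) and "there was no difference between the 2 groups before and after the training" (TUG) with wording that no statistically significant difference was found, followed by the estimate and interval.
3. Name the test and its sidedness beside the MMST p-value, and give its estimate and interval.
4. Base the strength and fall-risk statements in the Abstract and Conclusion on these between-group intervals.

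The cost is some plan wording and one extra output column from data already held; no new participants or measurements are needed. The price in presentation is that the MMST, strength and fall-risk results will look less certain.

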Each part of Nintendo Wii was introduced to the individuals in the training group in the first session and games were played with the support of a physiotherapist. How to play the selected games and their objectives were explained and taught to each individual by the physiotherapist in practice. The patient was supported with verbal and physical feedback when it was noticed that the patient made wrong movements during the games played in later sessions. Games that require serious strength, balance, and coordination such as Bird's eye Bull's eye, Obstacle Course, Balance Bubble, etc. were considered as a difficult activity for the patient and were not used in this study.

The difficulty of the games was set to the simplest level for each patient. Their difficulty level was increased as the patients became successful. The difficulty of the games was increased according to the classification determined by the Nintendo Wii device. The duration of each game was different, and the games were played until the end of their times. All games were played by the patients under the same conditions, in the same environment, at the same temperature and at the same time in each session.

The permission for the study was obtained from Karamanoğlu Mehmet Bey University Faculty of Health Sciences, Non-Invasive Clinical Research Ethics Committee. Voluntary consent forms were signed by both individuals with AD and caregivers of these individuals.

CONSORT 2010 Flow Diagram

Statistical Analysis Plan

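### Both conclusions forecast benefit from virtual reality and technology in general, but the trial tested selected Nintendo Wii games against no application in eligible residents of one nursing home

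*Combined protocol and SAP*

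**What the plan says.** **The claim.** The Conclusion first describes virtual reality in general terms, as a three-dimensional simulation that the user controls through special devices. It then says, of support for physiotherapy and rehabilitation programmes, that "technological developments and virtual reality applications will increase the success of treatment especially for muscle strength, walking speed, reduction of fall risk and cognitive functions". The Abstract's Conclusions end with the same forecast, without the list of outcomes. The sentence just before it in the Abstract says that the "virtual reality application in individuals with Alzheimer's dementia increased muscle strength and decreased the fall risk". The Conclusion closes more cautiously: "This training may work as well, and that the results indicate that it may reduce the risk of falls".

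**The intervention.** Under Study Procedure and Protocol, the training group was trained "with a Nintendo Wii virtual reality device 2 times a week for a period of 6 weeks, with 1 session lasting for 30 minutes", and every patient played the same games. Titles needing serious strength, balance and coordination "were considered as a difficult activity for the patient and were not used in this study". On the level of play, the section says: "The difficulty of the games was set to the simplest level for each patient"; the level was then raised as patients succeeded. The control group received no application and continued routine medical treatment.

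**The population.** The same section restricts entry to residents of one home aged 65–80 with mild or moderate Alzheimer's dementia, an MMST score of 18–24 and no communication problems. Exclusions include other neurological disease, cardiac and cerebrovascular events, endocrine disorders, depression, sensory loss and amputation.

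**The concern.** A conclusion should answer the question that the design put. Here the forecast covers a class of technology, is worded as a certainty (will increase), and carries no limit on device, comparator, setting, age or severity. The trial has data on one console, one set of games and one home.

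Conclusions are the part that readers carry away. A reader could apply this one to other virtual reality systems, to people whose cognition is below the entry limit, to people over 80 or to people living at home. The trial studied none of these. A reader could also take it as evidence for adding virtual reality to an existing physiotherapy programme, although the comparison was with no application.

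**Working it through.** No effect estimate changes, so the check sets the forecast beside the design and then verifies the counts.

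| Element | Forecast in the two conclusions | What was tested (Study Procedure and Protocol) |
|---|---|---|
| Intervention | Technological developments and virtual reality applications | One console and one set of games; the most demanding titles omitted; simplest starting level, raised with success |
| Role of the intervention | Support to physiotherapy and rehabilitation programmes | Wii training versus no application; no physiotherapy programme to which the games were added is described |
| Setting | Not limited | One nursing home |
| Age | Not limited | 65–80 |
| Severity | Not limited | Mild or moderate, MMST 18–24 |
| Outcomes named (Conclusion only) | Muscle strength, walking speed, fall risk, cognitive functions | Knee extension strength, TUG time in seconds, TFES, MMST; walking speed is not a listed measure |

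**Counts.** The section reports 38 people with an Alzheimer's diagnosis. One was not included for an MMST below 18, 3 for hearing or communication problems, and 2 because they did not want to start.

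- Losses: 1 + 3 + 2 = 6.
- Entered: 38 − 6 = 32, which reproduces the stated number.
- Share of those with a diagnosis: 32/38 = 84.2%.

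**Severity window.** MMST 18–24 covers 24 − 18 + 1 = 7 integer scores. On the section's own bands (0–17 severe, 18–23 mild, 24–30 normal), that is the whole mild band plus the lowest normal score. Nobody from the 0–17 band was eligible.

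**What narrowing alone would leave.** The Results report, after training:

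- Right and left knee extension strength: no significant difference between groups.
- TFES: no difference between groups (p > 0.05).
- TUG: no difference between groups (p > 0.05).
- MMST: higher in the training group (p = 0.049 in the Abstract).

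The significant changes in strength, TFES and TUG are changes from baseline within the training group. The randomised comparison did not show a benefit on these three measures. A sentence narrowed only by device and population, and still saying that strength rose and fall risk fell because of the training, would therefore report something that the between-group results do not establish.

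**The case against.** Several points on the other side are sound.

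- **The device, site and eligibility are stated openly.** The title and the Abstract's Purpose name the Wii, and the Abstract's Method gives the age range and mild or moderate disease. This stands, but the forecast drops these limits.
- **The Abstract's first conclusion sentence.** A reader might infer an unlimited claim about all people with Alzheimer's dementia. It is in the past tense and uses a definite article, so it plausibly refers to the application and patients described just above it. The documents do not support the wider reading of that sentence; the overreach in scope lies in the forecast that follows.
- **Only easy play was tested.** A reader might infer this from the omitted titles and the simplest starting level. It goes too far, because the level rose with success. What was not studied is the omitted titles.
- **Heavy selection.** A reader might divide 32 by the home's 90 older people and get 36%. That denominator is everyone in the home. Among those reported with a diagnosis, 84% entered, and none of the 6 losses is attributed to the cardiac, endocrine, depression or sensory-loss exclusions. Those criteria limit whom the result covers, but the documents do not show that they removed anyone.
- **The hedged closing sentence.** It is confined to this training and says may. It does not withdraw the forecast before it, and the Abstract has no such hedge.
- **Any small single-centre trial has limited reach.** True, and suggesting a possible implication would be acceptable. Asserting that untested systems will increase treatment success is not.

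**Conclusion.** The point holds for the forecast sentence in the Abstract's Conclusions and in the Conclusion. It goes beyond the trial on device, comparator, setting, age and severity. What was tested is one set of Wii games, twice weekly for 6 weeks, against no application, in 32 residents of one home within the stated limits. There are no data on any other system.

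This is a fault of wording. It changes no data, analysis or sample size, but it does change what the trial may claim to have concluded. It rests on reading the forecast at face value and on the eligibility rules having been applied as written. The 84% takes the 38 as the people with a diagnosis who were considered; the documents do not say whether these were all the residents with Alzheimer's dementia.

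A reader might also infer that the training has no effect on strength or falls. The documents do not support that either. A non-significant comparison with 16 per group leaves the benefit unproven; it does not show that there is none.

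**What to change.** In both conclusions, delete the reference to technological developments and the general virtual reality forecast. Replacement text could read:

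> In 32 residents of one nursing home aged 65–80 with mild or moderate Alzheimer's dementia and an MMST score of 18–24, who met the inclusion criteria and had none of the exclusion criteria, selected Nintendo Wii games played twice weekly for 6 weeks were compared with no application. After training, MMST scores were higher in the training group (p = 0.049). No significant between-group difference was found in knee extension strength, TFES or TUG. Other virtual reality systems, the omitted games, people outside these limits, people living in the community, and use as an addition to a physiotherapy programme were not studied.

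The Abstract's statement that strength increased and fall risk decreased should be brought into line with this text. Within-group changes may be reported if they are labelled as such. Walking speed should come out of the list, or be replaced by TUG time.

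The cost is the rewording of two conclusions. The downside is a narrower claim.
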